**Table 2 - Responder definition**

A patient will be considered a responder in Part A if:

- Hgb increases  $\geq 1.5$  g/dL from baseline (defined as the last Hgb value before administration of the first dose of study drug) at treatment assessment endpoint (defined as mean value from Weeks 23, 25, and 26) and
- The patient did not receive a blood transfusion from Week 5 through Week 26 (EOT), and
- The patient did not receive treatment for CAgD beyond what is permitted per protocol from Week 5 through Week 26 (EOT)

A list of excluded concomitant medications, as well as allowed concomitant medications with restrictions, is provided in [Section 6.2.6](#). Beyond the permitted concomitant medications, study drug, and transfusions, patients may receive no other therapies for the treatment of CAgD while enrolled in this study; patients requiring other treatment for their CAgD in Part A will be withdrawn from the study and counted as non-responders. These patients will not be eligible to participate in Part B.

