### **6.2.6 Concomitant medications**

Patients will refrain from participation in any other investigational study drug trial in which receipt of any investigational drug occurred within 5 half-lives or 30 days, whichever is longer, prior to Day 0 and during the entire study.

Treatment with rituximab monotherapy or rituximab combination therapies (eg, with bendamustine, fludarabine, ibrutinib, or cytotoxic drugs) is prohibited.

During Part A, patients will not take any prescription or over-the-counter medications/products until completion of the follow-up assessments, unless prescribed by the Investigator or another physician for the treatment of an AE.

As noted in [Section 5.2](#), concurrent administration of erythropoietin and/or a daily dose of corticosteroids (equivalent to  $\leq 10$  mg/day of prednisone) is acceptable provided the patient has been on a stable dose during the previous 3 months; concurrent use of B12, folate and iron supplementation is acceptable provided the patient has been on a stable dose during the previous 4 weeks.

Topical therapies without risk of systemic absorption may be allowed, and non-prescription medications for treatment of minor intercurrent illnesses (headache, viral upper respiratory tract infections, etc) are permitted at the discretion of the PI. Hormonal contraception in female patients is allowed provided patients are receiving stable treatment  $\geq 3$  months prior to Screening. Any medication taken by the patient during the study, along with its strength, frequency of dosing, and reason for its use, will be documented in the patient's source data and the eCRF.

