## 7 DATA ANALYSES AND SAMPLE SIZE

Data from Part A and Part B of this study will be analyzed and reported separately. A separate Statistical Analysis Plan (SAP) for each part of the study will be produced providing full details of all analyses to be performed for Part A and Part B. Should there be any differences between the analyses plan and methodology described within the SAP versus the clinical protocol, the SAP will take precedence.

For the purposes of regulatory submission, an interim analysis of the Part A data will be performed after all patients have completed Part A.

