1.2 OBJECTIVE AND ENDPOINTS

Table 2 - Objectives and endpoints

	Objectives	Endpoints
Primary	
 to determine whether BIVV009 administration results in a ≥ 1.5 g/dL increase in hemoglobin (Hgb) level and avoidance of transfusion in patients with primary CAD without a recent history of blood transfusion. 	
 responder rate: A patient is considered a responder if he or she did not receive a blood transfusion from Week 5 through Week 26 (end of treatment [EOT]) and did not receive treatment for CAD beyond what is permitted per protocol. Additionally, the patient's Hgb level must meet the following criterion: Hgb increased ≥ 1.5 g/dL from baseline (defined as the last Hgb value before administration of the first dose of study drug) at treatment assessment timepoint (defined as mean value from Weeks 23, 25, and 26)
Secondary	
 To assess the effect of BIVV009 on clinical events and laboratory parameters related to hemolysis and anemia in patients with primary CAD To assess the effect of BIVV009 on specific complications of CAD (acrocyanosis, Raynaud's syndrome, hemoglobinuria, and thromboembolism) To assess the effect of BIVV009 on quality of life (QOL) in patients with primary CAD To evaluate the overall safety and tolerability of BIVV009 in patients with primary CAD 	
 Mean change from baseline in Hgb at treatment assessment timepoint (mean of values at Week 23, 25, and 26) Mean change from baseline in bilirubin (excluding patients with Gilbert's Syndrome) at treatment assessment timepoint Mean change from baseline in QOL, as assessed by the change in Functional Assessment of Chronic Illness Therapy (FACIT)-Fatigue scale scores at the treatment assessment timepoint Mean change from baseline in lactate dehydrogenase (LDH) at the treatment assessment timepoint Incidence of solicited symptomatic anemia at EOT Incidence of treatment-emergent AEs (TEAEs) and serious AEs (SAEs) Change from baseline in clinical laboratory evaluations Change from baseline in SLE panel Change from baseline in vital signs Change from baseline in electrocardiogram (ECG) data Physical examination findings Serum disease-related biomarkers

	Objectives	Endpoints

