 - Cerebral infarction, occlusion, and stenosis of cerebral and precerebral arteries
 - Vascular syndromes of brain in cerebrovascular diseases, transient cerebral ischemic attacks, and related syndromes
- Any arterial events
 - Myocardial infarction
 - Mesenteric arterial thrombosis
 - Other arterial embolism and thrombosis

Medical review of medical history and AEs will ascertain thromboembolic events for analysis.

Normalization of Bilirubin

The normalization of bilirubin is defined as total bilirubin \leq upper limit of normal (ULN) (specified by the central lab).

Normalization of LDH

The normalization of LDH is defined as LDH value \leq ULN (specified by the central lab).

Normalization of Haptoglobin

The normalization of haptoglobin is defined as haptoglobin above the level of detection.

Normalization of Hemoglobin

The normalization of hemoglobin is defined as hemoglobin ≥ 12 g/dL. Hemoglobin ≥ 11 g/dL will also be investigated.

Hemolytic Breakthrough

Hemolytic breakthrough at any visit is defined as

- A decrease of 2 g/dL or more in Hgb from the last scheduled visit, and
- One of the followings:
 - An increase of LDH from the last scheduled visit,

- An increase of bilirubin from the last scheduled visit,
- A decrease in haptoglobin from the last scheduled visit.

Protocol Prohibited CAD Medications

The following concomitant medications are prohibited during the study treatment period in Part A:

- Rituximab alone or as part of combination therapy
- Cytotoxic drugs (such as fludarabine, bendamustine, ibrutinib, cyclophosphamide)
- Other investigational drugs

The efficacy endpoint (estimand) accounting for protocol prohibited CAD medication(s) use will be based on the eCRF questionnaire “Did the subject receive any prohibited medications since the last visit?” at post-baseline visits. The medical review for the list of prohibited medications will be reconciled with the eCRF questionnaire.

Pooling Sites for Analysis

Data from all investigational sites will be pooled for the analysis, unless specified otherwise.

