4.3 PRIMARY ENDPOINT(S) ANALYSIS

4.3.1 Definition of endpoint(s)

The primary endpoint is the responder rate, defined in [Section 1.2](#), and is a composite endpoint of the following components:

1. Free of post-baseline transfusion within the range of Week 5 and Week 26 visit dates;
2. Change from baseline in Hgb at treatment assessment timepoint is ≥ 1.5 g/dL,
3. Receive no protocol prohibited medications (defined in [Section 4.1](#)) within the range of Week 5 and Week 26 visit dates

Components 1 and 3 will be determined by the corresponding questions in eCRF at all visits (from Week 5 through Week 26) in Part A.

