4.3.2 Main analytical approach

The primary analysis of the primary endpoint is to compare the responder rate of the BIVV009 treatment arm with the placebo treatment arm via the COVID-adjusted Composite estimand as defined in [Table 6](#) below.

To reject the null hypothesis of no treatment difference, the two-sided p-value based on a stratified Cochran-Mantel-Haenszel (CMH) test must be < 0.05 . The test will be stratified by baseline hemoglobin ($<$ median baseline Hgb vs \geq median baseline Hgb) and geographic region (Japan/Australia, United States, Europe). In the case of completely unbalanced strata (all records within any strata fall within a single treatment arm), the CMH test will be stratified only by baseline hemoglobin.

Table 6 - COVID-adjusted composite estimand for primary analysis

COVID-adjusted Composite Estimand	
Population	FAS
Response variable	Responder if

COVID-adjusted Composite Estimand	
	
 Free of post-baseline transfusion within the range of Week 5 and Week 26 visit dates, and The change from baseline in Hgb at treatment assessment timepoint ≥ 1.5 g/dL, and Receive no protocol prohibited medications defined in Section 4.1 within the range of Week 5 and Week 26 visit dates
ICEs handling	
 Subjects who early discontinue study prior to Week 23, for reasons other than COVID, are considered non-responders Subjects with no Hgb data from Week 23, 25, and 26, for reasons other than COVID, are considered as non-responders If a subject has a COVID-related infusion gap (defined as 2 consecutive missed infusions due to COVID-19), transfusions received and protocol-prohibited CAD medications taken during the infusion gap and within the 5 weeks following the infusion gap will not be included in the responder derivation.
Measure of treatment effect	
 Odds ratio of the proportion of responders in BIVV009 and Placebo using the Cochran-Mantel-Haenszel test Subjects missing infusions at Week 23 and 25 due to COVID will have their Hgb at TAT imputed using multiple imputation with an MMRM approach.

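### Component 3 of the primary responder endpoint is cited as one rule and scored by a narrower one

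*SAP*

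**What the plan says.** **The definition that is cited.** SAP Part A 4.3.1 opens: "The primary endpoint is the responder rate, defined in" Section 1.2. Table 2 in that section requires that a responder "did not receive treatment for CAD beyond what is permitted per protocol". The third criterion in Protocol Table 2 is the same in substance and carries a Week 5 to Week 26 window. Protocol 6.2.6 sets the limits: concurrent erythropoietin or low-dose corticosteroid "is acceptable provided the patient has been on a stable dose during the previous 3 months". Medication prescribed to treat an adverse event is a separate exception.

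**The rule that is scored.** The same paragraph of SAP 4.3.1 lists component 3 by reference to Section 4.1, and Table 6 repeats it: "Receive no protocol prohibited medications defined in Section 4.1 within the range of Week 5 and Week 26 visit dates". Tables 7 and 8 do the same. Section 4.1 gives the content under "The following concomitant medications are prohibited during the study treatment period in Part A": rituximab alone or in combination, cytotoxic drugs, and other investigational drugs.

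**The data source.** SAP 4.3.1 adds: "Components 1 and 3 will be determined by the corresponding questions in eCRF at all visits" from Week 5 through Week 26. Section 4.1 describes the eCRF question as asking about any prohibited medication since the last visit, and says the medical review will be reconciled with the answer.

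**Precedence.** Protocol Section 7: "Should there be any differences between the analyses plan and methodology described within the SAP versus the clinical protocol, the SAP will take precedence".

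**The concern.** The first rule turns on the reason for treatment and on whether the protocol permits it. The second turns on membership of three drug classes. A treatment for the disease can be outside the protocol's permission without belonging to any of those classes. The operative section for the primary endpoint therefore names one definition and applies a narrower one. The protocol's precedence clause ranks the SAP above the protocol, so it cannot settle a conflict that lies within the SAP.

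At stake is the responder status of individual patients in a trial of 20 per arm, where one patient is 5 percentage points. If the difference is noticed only after unblinding, the choice of rule would be made with treatment arm known. The term prohibited medication also sets values to missing in the Hypothetical estimand for both key secondary endpoints (hemoglobin and FACIT-Fatigue, SAP 4.4.1.2), so the same wording matters there.

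**Working it through.** **1. The two rules side by side**

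| | Cited rule (SAP 1.2, Protocol Table 2) | Scored rule (SAP 4.3.1, 4.1, Tables 6 to 8) |
|---|---|---|
| Basis | Disease treatment not permitted by the protocol | Any of three listed classes |
| Window | Week 5 to 26 in the protocol; none attached to this clause in SAP 1.2 | Week 5 to Week 26 visit dates |
| Rituximab or a cytotoxic drug given for the disease in the window | Fails | Fails |
| Corticosteroid or erythropoietin newly started for the disease in the window, not for an adverse event | Fails | Not on the list |

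**2. Who is affected.** A patient changes status only if all of these hold:
- the treatment was for the disease, was not permitted and was not listed;
- the patient was not withdrawn before Week 23 (Table 6 scores non-COVID discontinuation before Week 23 as non-response);
- the mean hemoglobin rise over Weeks 23, 25 and 26 was at least 1.5 g/dL;
- there was no transfusion that counts against response from Week 5.

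**3. Whether another analysis tests it.** Sensitivity analyses I to III reuse component 3 as scored. Analysis IV uses the same response variable in the per-protocol set, and the exclusion for prohibited treatment in SAP 4.2 also points to Section 4.1. The by-arm summary of the three criteria follows the same rule. Concomitant-medication tables and deviation summaries could show such use, but only descriptively.

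**4. Size.** The documents give no frequency, so this is an illustration. Inputs from Protocol 7.10: 20 per arm, 85% v 35%, two-sided 5% level. Expected responders are 0.85 × 20 = 17 and 0.35 × 20 = 7. The stated 87% power reproduces: exact enumeration with Fisher's test gives 0.875. An unstratified Mantel-Haenszel test gives 0.928.

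The statistic is (a − E)²/V, with a the BIVV009 responders, m all responders, E = m/2, and V = 20 × 20 × m × (40 − m)/(40² × 39). For 17 v 7: m = 24, E = 12, V = 153,600/62,400 = 2.4615, so the statistic is 25/2.4615 = 10.156.

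| Responders, BIVV009 v placebo | Statistic | p |
|---|---|---|
| 17 v 7 (planned) | 10.156 | 0.0014 |
| 16 v 7 (one BIVV009 responder reclassified) | 8.079 | 0.0045 |
| 15 v 7 (two reclassified) | 6.303 | 0.012 |
| 17 v 6 (one placebo responder reclassified) | 12.069 | 0.0005 |
| 14 v 7 | 4.789 | 0.029 |
| 13 v 7 (one BIVV009 responder reclassified) | 3.510 | 0.061 |

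Over all outcomes at 85% v 35%, 7.4% are significant but would be lost if one BIVV009 responder were removed. A further 3.4% are not significant but would be gained if one placebo responder were removed. Both figures assume that such a patient exists.

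**The case against.** **The scored rule is not in doubt.** Section 1.2 is a summary table, while 4.3.1 and Tables 6 to 8 all point to the list. It stands that a programmer would use the list. But 4.3.1 itself names Section 1.2 as the definition, so following the list can produce a responder who fails the definition it cites.

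**Most such patients are caught anyway.** Protocol 4.1 says patients requiring other disease treatment in Part A are withdrawn and counted as non-responders. The eCRF question is not worded by class, so a site could answer yes for an unlisted drug, and a medical review follows. This largely stands. The gaps are patients not withdrawn (Protocol 5.3 says non-permitted intake may lead to withdrawal) and patients treated from Week 23 on. The review is tied to the list, and the SAP does not say which source prevails.

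**A patient needing new treatment is unlikely to meet the other two criteria.** This stands as a reason to expect few cases. Protocol 2.2 also describes the disease as typically unresponsive to steroids.

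Three stronger readings are not supported. A reader might infer that the list also fails patients given a listed drug for another illness; that is thin, because SAP 4.1 heads the list as CAD medications. A reader might infer that the eCRF look-back brings in use before Week 5; SAP 4.3.1 already limits the component to the Week 5 to Week 26 visit dates. A reader might also take the 7.4% as the chance of a wrong conclusion; it describes only how often a 40-patient result turns on one patient, whatever the cause.

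**Conclusion.** The inconsistency is real and sits inside SAP Part A: the primary endpoint cites one definition of component 3 and scores a narrower one. It is a moderate point that should be fixed. The affected group is probably small and its frequency is unknown. At the planned result, one or two reclassified BIVV009 responders do not alter the conclusion; near the boundary one can. The direction depends on the arm: reclassifying a BIVV009 responder weakens the result and reclassifying a placebo responder strengthens it.

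The p-values are unstratified, whereas the planned test is stratified by baseline hemoglobin and region. A simulation of the stratified test, with an assumed 20/20/60 region split and strata unrelated to outcome, gives 7.6% and 4.1% in place of 7.4% and 3.4%. The documents do not show that unlisted treatment will go unscored in practice, nor that the trial's conclusion is at risk; they show that the plan leaves the classification open.

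**What to change.** Before unblinding, reconcile Protocol Table 2, Protocol 6.2.6 and SAP Part A 1.2, 4.1 and 4.3.1 so that component 3 has one definition and one Week 5 to Week 26 window, consistent with the responder definition the SAP cites. The sponsor should state which medicines count. Apply the definition by blinded review of the dated concomitant medications, and state in advance how a disagreement with the eCRF answer is resolved; which source prevails is the sponsor's choice. Report by arm any patient whose component 3 status differs between the two wordings. Say whether the same meaning applies to prohibited medication in the key secondary estimands.

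As an editorial item, correct SAP Table 3, which points to Section 5.1.1 for the list; Section 5.1 is the list of abbreviations.

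The cost is SAP wording and one blinded review. Concomitant medications are already recorded at every visit (Protocol Table 3), and sponsor personnel other than drug supply are blinded until the Part A analysis (SAP 1.1). No new data are needed.

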4.2 PARTICIPANT DISPOSITIONS

The number (%) of participants included in each of the analysis populations listed in [Table 4](#) will be summarized.

The number of subjects with the status of completed, and discontinued study treatment early, including the primary reason for those who discontinued, will be tabulated for the FAS in Part A. In particular, the number of subjects who early discontinue study and the number of subjects with a missing dose due to COVID-19 will be presented. Subject disposition, including the date of the last visit and the reason for early termination for subjects who did not complete the study treatment, will be provided in a data listing.

Additionally, subject enrollment by country and site as well as the number and percentage of subjects attending each planned visit will be summarized for the FAS.

Protocol deviations

All protocol deviations will be recorded throughout the study and will be medically adjudicated and categorized into major and minor. Deviations due to COVID-19 will be adjudicated and identified as such. Major and minor protocol deviations/violations are to be pre-specified prior to database lock. All major protocol deviations will be summarized for the FAS.

Important protocol deviations (within Part A study treatment period) impacting efficacy assessment are defined as any of the following:

- Not meeting eligibility inclusion criterion #3 as in the protocol,
- Missing at least 2 consecutive doses or 3 intermittent doses,
- Received protocol prohibited CAD treatment ([Section 4.1](#)),
- Free of transfusion after Week 5 but missing hemoglobin assessments at all three visits of Weeks 23, 25, and 26.

Important protocol deviations will be summarized for the FAS. Subjects who have had any of the important protocol deviations will be excluded from the PP population.

4.3 PRIMARY ENDPOINT(S) ANALYSIS

4.3.1 Definition of endpoint(s)

The primary endpoint is the responder rate, defined in [Section 1.2](#), and is a composite endpoint of the following components:

1. Free of post-baseline transfusion within the range of Week 5 and Week 26 visit dates;
2. Change from baseline in Hgb at treatment assessment timepoint is ≥ 1.5 g/dL,
3. Receive no protocol prohibited medications (defined in [Section 4.1](#)) within the range of Week 5 and Week 26 visit dates

Components 1 and 3 will be determined by the corresponding questions in eCRF at all visits (from Week 5 through Week 26) in Part A.

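### Transfusion and prohibited-medication components of the primary endpoint are defined by date from Week 5 but scored from visit questions that can reach back before Week 5

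*SAP*

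**What the plan says.** SAP 4.3.1 defines component 1 as "Free of post-baseline transfusion within the range of Week 5 and Week 26 visit dates". Component 3 requires no prohibited medication "within the range of Week 5 and Week 26 visit dates". The sentence after the list gives the scoring source: "Components 1 and 3 will be determined by the corresponding questions in eCRF at all visits (from Week 5 through Week 26".

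SAP 4.1 bases the medication limb on the eCRF question "Did the subject receive any prohibited medications since the last visit" and adds "The medical review for the list of prohibited medications will be reconciled with the eCRF questionnaire". The transfusion question is not reproduced in either document.

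Protocol Table 2 uses the same window for both limbs. Its transfusion limb reads "The patient did not receive a blood transfusion from Week 5 through Week 26 (EOT". Its limb on other CAgD treatment has the same start and end. Two other places differ on the treatment limb:

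- The protocol synopsis and the text under Table 2 say that patients who need other CAgD treatment in Part A are withdrawn and counted as non-responders. No Week 5 lower limit is given.
- SAP Table 2 ties the transfusion limb to Week 5 but puts no time limit on the treatment limb.

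SAP Table 6 disregards transfusions and prohibited medications during a COVID-related infusion gap and in the 5 weeks after it. Under Protocol section 7, the SAP prevails where it differs from the protocol.

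**The concern.** The primary endpoint has a definition bounded by dates and a scoring sentence bounded by visits, and the two need not agree. A question that looks back from the Week 5 visit reports on the interval before the window. A patient transfused on Day 28 and never again meets component 1 by definition, but could answer yes at Week 5 and fail it by the scoring sentence.

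Such a patient is plausible. Entry requires hemoglobin of 10.0 g/dL or less, the transfusion criteria begin below 9 g/dL with symptoms, and transfused patients stay in the study. With about 20 patients per arm, a few reclassifications could matter, so the rule should not be left to whoever programs the derivation.

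**Working it through.** **Inputs.** Scheduled visits at Day 21 (Week 3), Day 35 (Week 5) and Day 182 (Week 26), each ±2 days (Protocol Table 3); 20 patients per group, response rates 85% and 35%, two-sided 5% test, stated power 87% (Protocol 7.10).

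**1. The plan's own figure.** Power = Σₐ Σ_b Bin(a; 20, 0.85) · Bin(b; 20, 0.35) · 1[p(a,b) < 0.05], by exact enumeration. Fisher's exact test gives 87.5%, which reproduces the stated 87%. An unstratified CMH test gives 92.8%. The present point does not change either figure; they are the base for step 5.

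**2. Reach of the Week 5 answer.**
- Nominal: 35 − 21 = 14 days.
- Shortest: Week 5 on Day 33, Week 3 on Day 23, so 33 − 23 = 10 days.
- Longest: Week 5 on Day 37, Week 3 on Day 19, so 37 − 19 = 18 days.

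This assumes no unscheduled visit in between. The window by definition is 182 − 35 = 147 days. Counting from Week 3 makes it 182 − 21 = 161 days, and 161/147 − 1 = 9.5% longer.

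**3. Information in that answer.** An answer given at Week 5 cannot report later events, and Protocol 6.1.3 has the record taken before that day's infusion. Apart from events on the visit day itself, it can add only events that the definition excludes.

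**4. Definition and literal scoring side by side** (hemoglobin criterion met, no COVID gap, transfusion question assumed to look back):

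| Only transfusion | Component 1 by date | Component 1 by answers from Week 5 |
|---|---|---|
| Day 14 | met | met |
| Day 28 | met | failed |
| Day 42 | failed | failed |

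**5. Possible effect on power.** The documents give no event rate for Weeks 3 to 5. Assume a share q of would-be responders is lost, so each rate becomes p(1 − q):

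| Loss assumed | BIVV009 / placebo rate | Fisher | Unstratified CMH |
|---|---|---|---|
| none | 85.0% / 35.0% | 87.5% | 92.8% |
| 2% in both arms | 83.3% / 34.3% | 85.0% | 91.0% |
| 5% in both arms | 80.75% / 33.25% | 80.8% | 88.1% |
| 10% in both arms | 76.5% / 31.5% | 73.6% | 82.7% |
| 5% in BIVV009 only | 80.75% / 35.0% | 77.7% | 85.6% |
| 5% in placebo only | 85.0% / 33.25% | 89.7% | 94.2% |

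One patient reclassified is 1/20 = 5 percentage points in that arm.

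**6. Medication limb.** Here the look-back is documented, but the definition is not uniform. Protocol Table 2 and SAP 4.3.1 start at Week 5. The protocol text under Table 2 and in the synopsis makes need for other CAgD treatment at any time in Part A a non-response, and SAP Table 2 sets no start. Whether a Week 3 to 5 event should count depends on which text is followed.

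**7. COVID waiver.** Table 6 needs an event placed inside or outside a gap plus 5 weeks. A yes/no answer covering an interval between visits cannot do that when a boundary falls within the interval.

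**The case against.** The strongest reply is that the scoring sentence only names a data source and is subject to the definition just above it. The date-bounded wording recurs in the SAP's estimand tables. Other analyses need transfusions placed in time: SAP 4.3.2 tabulates them before Week 5 and from Week 5 to Week 26, and SAP 4.5.1 analyzes time to first transfusion both with and without the first 5 weeks. A date-based derivation is therefore possible, and a careful programmer might use one. That stands, and it is why the literal scoring *can*, rather than *will*, misclassify a patient. But no text says that dates govern the endpoint, and the reconciliation in SAP 4.1 covers medications only and states no date rule.

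Second, the look-back wording is known only for medications. That also stands: for transfusions it is an inference.

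Third, a patient withdrawn before Week 23 for other CAgD treatment is a non-responder under SAP Tables 6 and 7 anyway (for non-COVID reasons), so for medications the result may seldom change. This is fair, and component 3 needs reconciling before it is re-specified.

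A reader might infer from 14/35 = 40% of the first 5 weeks that 40% of patients transfused only early would be misclassified, or that the rule works against BIVV009. Neither is supported. The first needs an even spread of early transfusions and a look-back transfusion question, neither of which is documented. For the second, the placebo-only row in step 5 shows that the effect can run the other way.

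**Conclusion.** The point holds as an unresolved conflict between definition and scoring in the primary endpoint, not as a demonstrated misclassification. Read literally, the SAP scores a window that reaches a nominal 14 days (10 to 18) before the one it defines. This is documented for prohibited medications and conditional for transfusions. The number of patients affected and the direction of bias are unknown. Under an assumed equal loss of 2% to 10% of responders, power by Fisher's test would fall from 87.5% to between 85.0% and 73.6%; a loss confined to placebo would raise it.

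The waiver problem matters only if the COVID-adjusted estimand is used. SAP 4.3.2 reverts to the unadjusted composite estimand if no patient missed both the Week 23 and Week 25 visits because of COVID-19.

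The change should be made because the rule concerns the primary endpoint, can be settled while treatment is still blinded, and costs little.

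**What to change.** Replace the scoring sentence in SAP 4.3.1 with a rule along these lines:

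> Component 1 is derived from recorded transfusion dates. A transfusion counts if its date lies from the Week 5 visit date (Study Day 36 if that visit was missed) through the Week 26 visit date. The Table 6 waiver is applied by date. The eCRF visit questions are a cross-check only; a positive Week 5 answer does not by itself fail the component.

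Add a rule for partial dates. The SAP's only statement on these, in 4.1, sits with time-to-event variables and leaves them unknown. One workable rule is to bracket the event by the visit answers and, if it still cannot be placed, to count it as inside the window in both arms.

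Derive component 3 from medication dates in the same way, but first reconcile the Week 5 start in Protocol Table 2 and SAP 4.3.1 with the synopsis, the text under Protocol Table 2, and SAP Table 2. Which of these should apply is for the sponsor to settle; the derivation then follows it.

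The cost is a short SAP edit and one derivation, made before unblinding for the Part A analysis. No new data should be needed: Protocol 6.1.3 records medications and transfusions at every visit, and the SAP's other transfusion analyses already presuppose their timing. The form itself is not in the documents, so the presence of date fields should be confirmed.
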